**Clinical Study Protocol**  
**Johnson & Johnson Vision Care, Inc.**

Visit 1: Treatment 1 Lens Fitting		
Step	Procedure	Details
1.22	General Lens Fit Assessment	
Evaluate lens centration, movement on blink, and push-up test for each eye.
 
An unacceptable fit is deemed by one of the following criteria:
 
 
• limbal exposure at primary gaze or with extreme eye movement.
 
• edge lift.
 
• excessive movement in primary and up gaze.
 
• insufficient movement in all three of the following conditions: primary gaze, up gaze, and push-up test.
 
 
Note: if lens fit is unacceptable for either eye, the subject will be discontinued from the study.

1.23	White Light Lens Surface Wettability	Record the white light lens wettability of both lenses.
1.24	Visual Acuity	Record the distance visual acuity with the contact lenses (OD, OS, and OU) to the nearest letter. Smaller lines must be shown until the subject incorrectly identifies at least 50% of the letters.
1.25	Continuance	
For the subject to continue in the study, they must meet all three of the following criteria:
 
 
• Visual acuity is 20/30 or better OD and OS.
 
• The lens fit is acceptable OD and OS.
 
• Investigator approval.
 
 
If the Investigator does not approve the dispensing of the first study lens, then the study is terminated for that subject.

**Clinical Study Protocol**  
**Johnson & Johnson Vision Care, Inc.**

Visit 1: Treatment 1 Lens Fitting		
Step	Procedure	Details
1.26	Dispense	
The lenses will be dispensed for 13-15 days
 
 
1. The subjects should wear their lenses similar to the inclusion criteria: <math>\geq 6</math> hours per day, <math>\geq 5</math> days per week.
 
2. The lenses will be worn as daily wear daily disposable only.
 
3. All subjects will be provided a bottle of ACUVUE RevitaLens to return any problematic lenses to the investigational site.
 
4. Rewetting drops are permitted if needed.
 
5. A patient instruction booklet will be provided.
 
 
Note 1: Ensure that the subject has enough lenses to last them to their next scheduled visit with no extras. In the event a lens is lost or damaged, and the subject has run out of lenses, the subject will return to the investigator site for replacement.
 
Note 2: The subject's habitual contact lenses cannot be worn at any time during the study.
 
Note 3: Remind the subjects to bring back any unworn lenses to the next visit.
 
Note 4: Remind the subject to bring a habitual form of correction to next visit.

1.27	Schedule next visit	
Schedule the follow-up visit to occur in <math>14 \pm 1</math> days (counting the day of this visit as day 0, the subject may return on day 13 through 15).

# Clinical Study Protocol

## Johnson & Johnson Vision Care, Inc.

### VISIT 2

The follow-up will occur 13-15 days after Visit 1. The subjects must enter the visit wearing their study contact lenses.

Visit 2: Treatment 1 Follow-Up 1															
Step	Procedure	Details													
2.1	Adverse Events and Concomitant Medications Review	Review any changes to the subject's medical history or concomitant medications from the previous study visit. Record any changes, and any adverse events.													
2.2	Wearing Time	Record the average wearing time and comfortable wearing time.													
2.3	Compliance	Confirm compliance with the prescribed wear schedule.													
2.4	Return unworn lenses	Collect any unworn study lenses from the subject.													
2.5	Subject Reported Ocular Symptoms	Subjects will respond to a verbal open-ended symptoms questionnaire.													
2.6	Follow-Up Questionnaire	Subjects will respond to the following questionnaires: 1. CLUE Follow-up 2. GSI Product Performance 3. Lens preference to habitual													
2.7	Distance ETDRS LogMAR Visual Acuity	
Measure monocular distance high luminance high contrast (HLHC) visual acuity using ETDRS charts at 4 meters.
 
Measure each eye once using the charts shown in the table below:
 
  
 Condition	HLHC	
   
 Room illumination	> 400 lux	
 
 Chart luminance	120 - 200 cd/m^2	
 
 Eye	OD	OS	
 
 Charts	HC-1	HC-2	
  
 
Recorded letter-by-letter results into EDC.
	Condition	HLHC	Room illumination	> 400 lux	Chart luminance	120 - 200 cd/m 	Eye	OD	OS	Charts	HC-1	HC-2	
Condition	HLHC														
Room illumination	> 400 lux														
Chart luminance	120 - 200 cd/m 														
Eye	OD	OS													
Charts	HC-1	HC-2													
2.8	Visual Acuity	Record the distance Snellen visual acuity with the contact lenses (OD, OS, and OU) to the nearest letter. Subjects must read the smallest line until at least 50% of the letters are read incorrectly.													

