### **5.2. Masking**

This is a single-masked trial. The investigators may be aware of the study lenses based on a slight difference in lens color (the Test lenses will be slightly more turquoise in color than the Control lens).

Masking will be used to reduce potential bias. Subjects will be unaware of the identity of the investigational product. Investigators and clinical site personnel involved in the data collection will not be masked as to the identity of the investigational product.

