### **14.2. Sample Size Justification**

This study is designed and powered to demonstrate non-inferiority of the Test lens compared to the Control lens with respect to the primary endpoints: slit lamp findings, fit acceptance, distance monocular logMAR VA, and CLUE overall quality of vision. Sample size was estimated to achieve a minimum statistical power of 80% for logMAR VA and CLUE vision with a 2-sided type I error of 0.05 each, and a minimum statistical power of 80% for slit lamp findings and lens fit acceptance with the 95% central posterior credible interval. For information purpose, power was estimated for the secondary endpoints using the sample size determined by the primary endpoints.

Sample size/power estimation was based on historical hard-lock data from [REDACTED] and [REDACTED] [REDACTED] and the interim read data from [REDACTED]. The same type of Test and Control lenses were investigated in [REDACTED] and [REDACTED] with a 2×2 crossover design. Test lenses in [REDACTED] were made from the pilot line while Test lenses in [REDACTED] and the current study are produced from the manufacturing line. [REDACTED] is a 6×6 crossover study with 6 different types of lenses.

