# Clinical Study Protocol

## Johnson & Johnson Vision Care, Inc.

█ (Interim) for period 1, it was assumed that the percentage of subjects preferring Test lens was 0.4, the percentage of subjects preferring Habitual lens was 0.2, and the percentage of subjects with no preference was 0.4. A total of 2000 replicating trials were simulated. To estimate statistical power, the simulated multinomial data were analyzed using a generalized linear regression model with a generalized logit link function and tested for statistical superiority (preference ratio of preferring Test to Habitual).

Table 11 below summarizes the required number of completed subjects to achieve a minimum of 80% statistical power for the primary endpoints. Table 12 shows the statistical power for the secondary endpoints based on the sample size determined by the primary endpoints.

Table 11: Sample Size Estimation for the Primary Endpoints

Endpoint	Hypothesis Testing	Sample Size	Power
Monocular Distance LogMAR VA	Non-inferiority	16	84%
CLUE Vision	Non-inferiority	286	80%
Lens Fit Acceptance	Non-inferiority	140	83%
Slit Lamp Findings	Non-inferiority	240	83%

Table 12: Power Estimation for the Secondary Endpoints

Endpoint	Hypothesis Testing	Sample Size	Power
CLUE Comfort	Non-inferiority	286	73%
CLUE Handling	Non-inferiority	286	23%
Situational Visual Performance – Indoor (Clarity of Vision Indoors in Bright Light)	Non-inferiority	286	93%
Situational Visual Performance – Digital Devices (Overall Preference While Using Computer Screens & Digital Devices)	Superiority	143 for Test Lens Group	88%

As indicated in Table 11 above, the sample size chosen for this study was primarily driven by the primary endpoint of CLUE overall quality of vision in order to achieve a statistical power of at least 80% for all primary endpoints. The plan is to enroll approximately 320 eligible subjects with a target of 286 to complete the study (143 per arm).

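### At Visit 2, unmasked staff review adverse events, compliance and symptoms with the subject before the CLUE and preference questionnaires, an avoidable route for bias into the self-reported endpoints

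*Combined protocol and SAP*

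**What the plan says.** Section 7.2 numbers the start of Visit 2 as follows:

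- 2.1, adverse event and medication review: "Record any changes, and any adverse events".
- 2.2, average and comfortable wearing time.
- 2.3, compliance: "Confirm compliance with the prescribed wear schedule".
- 2.4, return of unworn lenses.
- 2.5, symptoms: "Subjects will respond to a verbal open-ended symptoms questionnaire".
- 2.6, questionnaires: "Subjects will respond to the following questionnaires: 1. CLUE Follow-up 2. GSI Product Performance 3. Lens preference to habitual".

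Acuity, lens fit, wettability, deposits, lens removal and slit lamp examination come after that, at steps 2.7–2.13.

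On masking, Section 5.2 says of subjects: "Subjects will be unaware of the identity of the investigational product". Of staff it says: "Investigators and clinical site personnel involved in the data collection will not be masked as to the identity of the investigational product".

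CLUE overall quality of vision is a primary efficacy endpoint (Section 2.2). Section 14.2 states that "the sample size chosen for this study was primarily driven by the primary endpoint of CLUE overall quality of vision". The four secondary endpoints (CLUE handling, CLUE comfort, indoor clarity and digital-device preference) are also subject self-reports.

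**The concern.** Subject masking protects a self-reported outcome best when the subject answers before talking to anyone who knows the assignment. Here five interactions with site staff are printed immediately before the questionnaires, and the last is a spoken discussion of symptoms. Two things can follow. Staff who know the lens may convey something about it, by how they ask or react. Separately, talking about problems can colour the ratings that come next, whichever lens was worn.

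Adjustment for baseline does not remove the first effect. Baseline CLUE is step 1.8 of Visit 1, before assignment (step 1.16) and before the Visit 1 symptoms questionnaire (step 1.21). A cue that depends on assignment can reach only the follow-up score. The Section 14.5 model (baseline score, lens type, random site) would attribute it to the lens.

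At stake is the non-inferiority conclusion on CLUE vision, which must be met for the study to succeed (Section 2.3). A shift toward Test makes a false claim more likely, and a shift against Test costs power.

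**Working it through.** **Inputs for CLUE vision.** From Section 14.2: margin −5, planned true difference (Test − Control) +2, common SD 21, 143 completers per arm, error rate "with a 2-sided type I error of 0.05 each". For non-inferiority this is one-sided 0.025. The documents give no figure for an interview-induced shift, so the shift *b* in the Test − Control difference below is an assumption, varied from −2 to +2 points.

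**Reproducing the plan's figure.** The distance from the planned difference to the margin is 2 − (−5) = 7.

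- Normal approximation: n per arm = 2 × 21² × (1.960 + 0.842)² / 7² ≈ 141.3, rounded up to 142.
- Two-sample t test (noncentral t, 284 degrees of freedom): 143 per arm, 286 in total, with power 80.2%.

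This agrees with Table 11 (286, 80%). The same table gives 240 for slit lamp findings, 140 for lens fit and 16 for logMAR acuity, so CLUE vision does set N.

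**Effect of an assumed shift.** SE = 21 × √(2/143) = 2.483.

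- False non-inferiority rate when the true difference is −5: approximately P(Z > 1.96 − b/2.483).
- Power when the true difference is +2: noncentral t with noncentrality (7 + b)/2.483.

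| Assumed shift b (points, + favours Test) | False non-inferiority at true −5 | Power at true +2 |
|---|---|---|
| −2 | 0.3% | 52% |
| −1 | 0.9% | 67% |
| 0 | 2.5% | 80% |
| +1 | 6.0% | 89% |
| +2 | 12.4% | 95% |

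A half-point shift toward Test gives 3.9% in the first result column (normal approximation).

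**Where a shift could come from, by endpoint.**

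- *CLUE vision, comfort and handling, and indoor clarity.* These are Test–Control contrasts, and both arms follow the same steps. Priming common to both arms largely cancels, so *b* differs from zero only if staff act differently by arm.
- *Digital-device preference.* Section 14.6 analyses this within the Test group, as preference for the Test lens against the habitual lens. There is no Control contrast in which common priming could cancel. Lens masking does not help either, since subjects know which lenses are the study lenses. A problem-focused conversation just beforehand could work against the Test lens here.

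**The case against.** The strongest reply is that the visible text does not show how these steps are run. It does not say who conducts step 2.5, whether probing is allowed, how CLUE is completed, or that the numbered order is binding. Appendix D lists procedures for patient-reported outcomes and for subject-reported symptoms; both are redacted and may contain safeguards. This stands as a limit: nobody can say from these documents that subject masking is the only protection, or that staff will probe or cue. It does not change the order printed in Section 7.2.

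Second, the plan already gets part of the sequence right. The questionnaires precede every examination at steps 2.7–2.13, so clinical findings at that visit cannot colour the answers. Medical history and wearing time also precede CLUE at baseline (steps 1.3 and 1.5), and moving step 2.6 to the front loses that parallel. Both points are fair. The symptoms questionnaire, however, has no counterpart before the baseline CLUE.

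Third, a reader might infer that the exposure exists only at Visit 2, so that reordering would restore the protection of masking. The documents do not support this. After assignment at Visit 1, unmasked staff handle the fitting and over-refraction, take the same verbal symptoms questionnaire, assess fit and instruct the subject (steps 1.16–1.27). All of that precedes the follow-up CLUE.

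Fourth, a reader might take the 6.0% as the plan's actual error rate, or assume that the bias favours Test. Neither follows. The shift is assumed, the documents give no evidence that staff behave differently by arm, and the direction could be either.

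Finally, Table 5 lists symptoms above the follow-up questionnaires, which might seem to confirm the order. It also lists slit lamp above them, although that is step 2.13. The table is not chronological and shows nothing either way.

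**Conclusion.** The point holds as an avoidable weakness in the order of Visit 2, not as a demonstrated bias. Three facts carry it: the printed step order, the unmasked staff, and the dependence of N = 286 on a self-reported endpoint.

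The size for CLUE vision is conditional. It rests on SD 21, 143 completers per arm, and an assumed one-point shift that needs staff to behave differently by arm. The two columns of the table also refer to different true differences: the error rates apply at the −5 margin, the power figures at the planned +2. For the preference item no differential behaviour is needed, but the documents give no basis for a size there.

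It would go too far to say that no later analysis could reveal such an effect. What can be said is that the planned CLUE model does not separate it from a lens effect, so prevention is the better course.

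**What to change.** Make the step 2.6 questionnaires the first activity of Visit 2. The subject completes CLUE, GSI and preference unaided on arrival, wearing the study lenses, before steps 2.1–2.5. Subjects already have to arrive in their study lenses, so nothing else in the visit has to change. State that this order is required, and put the eCRF pages in the same order. Table 5 can stay as it is. If the redacted patient-reported-outcomes procedure already governs how the forms are completed, cite it in step 2.6.

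The cost is a minor protocol and eCRF edit with the usual IRB review. Visit content and N = 286 are unchanged. The change reduces the influence of unmasked staff on the self-reports but does not remove it, because the contact at Visit 1 after assignment remains.

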**Clinical Study Protocol**  
**Johnson & Johnson Vision Care, Inc.**

Visit 2: Treatment 1 Follow-Up 1		
Step	Procedure	Details
2.9	Subjective Lens Fit Assessment	
Evaluate overall lens fit acceptance (acceptable or unacceptable) based on centration, movement and other fitting characteristics.
 
An unacceptable fit is deemed by one of the following criteria:
 
 
• limbal exposure at primary gaze or with extreme eye movement.
 
• edge lift.
 
• excessive movement in primary and up gaze.
 
• insufficient movement in all three of the following conditions: primary gaze, up gaze, and push-up test.
 
 
Note: if lens fit is unacceptable subject will be discontinued from the study.

2.10	Wettability Characteristics	Record the white light lens wettability of both lenses.
2.11	Surface Deposits	Record any front and back surface lens deposits.
2.12	Lens Removal	Both lenses will be removed and discarded.
2.13	Slit Lamp Biomicroscopy	
FDA Slit Lamp Classification Scale will be used to grade the findings. If no slit lamp finding is noted on the EDC form it is considered as a zero “0” grade for all observations listed.
 
Note: If the subject has Grade 3 or 4 slit lamp findings on the FDA scale, then they must be followed as an adverse event.
 
Adverse events must be reported to the JJVC monitors immediately.
 
Limbal and Bulbar Conjunctival Hyperemia findings (████) and Corneal Staining Assessment (████) will be emphasized using a more detailed scale.
 
After the slit lamp examination, at the discretion of the Investigator, rinse the subject’s eyes thoroughly with rewetting drops or saline.

# Clinical Study Protocol

## Johnson & Johnson Vision Care, Inc.

### FINAL EVALUATION

The final evaluation will ordinarily take place immediately following the last scheduled follow-up visit per the study protocol. It may also take place at any point the subject discontinues the study or is terminated from the study.

Final Evaluation			
Step	Procedure	Details	
F.1	Final Exam Form	Indicate if the subject completed the study successfully. If subject discontinued from the study, indicate the reason.	
F.2	Keratometry	Record the keratometry readings OD and OS in diopters. This can come from any appropriate instrument so long as the same instrument was used at the Baseline Evaluation.	
F.3	Exit Refraction	
Perform bare-eye subjective spherocylindrical refraction with a phoropter and record the best-corrected distance visual acuity (OD, OS and OU) to the nearest letter.
 
Note: This step is not necessary if the subject was exited due to screen failure.
	

**Clinical Study Protocol**  
**Johnson & Johnson Vision Care, Inc.**

Final Evaluation		
Step	Procedure	Details
F.4	Exit Slit Lamp Biomicroscopy (for subjects that are discontinued early)	
FDA Slit Lamp Classification Scale will be used to grade the findings. If no slit lamp finding is noted on the EDC form it is considered as a zero “0” grade for all observations listed.
 
Note: If the subject has Grade 3 or 4 slit lamp findings on the FDA scale, then they must be followed as an adverse event. Adverse events must be reported to the JJVC monitors immediately.
 
Limbal and Bulbar Conjunctival Hyperemia findings [REDACTED] and Corneal Staining Assessment [REDACTED] will be emphasized using a more detailed scale.
 
If the clearance of the fluorescein needs to be expedited, preservative-free rewetting drops or saline may be instilled. This step is not necessary if the subject was exited due to screen failure.
 
Note: This step is not necessary if the subject was exited due to screen failure, or if biomicroscopy was performed as part of the final follow-up visit procedures (i.e., immediately prior to the final evaluation).

### 7.3. Unscheduled Visits

If, during the investigation, a subject requires an unscheduled visit to the clinical site, the following information will be collected, as appropriate:

- Chief complaint prompting the visit. If the reason is an adverse event, the applicable eCRF for the adverse event must be completed and subject record completed as appropriate.
- Date and time of the visit and all procedures completed at the unscheduled visit.
- Review of adverse event and concomitant medications.
- Documentation of any test article dispensed or collected from the subject, if applicable.
- Slit lamp findings (using the Slit Lamp Classification Scale).

If the Investigator withdraws a subject from the study, the final study visit case report forms must be completed indicating the reason(s) why the subject was withdrawn. The subject record must be completed documenting the date and primary reason for withdrawal and the study CRA notified.

# Clinical Study Protocol

## Johnson & Johnson Vision Care, Inc.

Any ocular and non-ocular Adverse Events that are ongoing at the time of the study visit will be followed by the Investigator, within licensure, until they have resolved, returned to pre-treatment status, stabilized, or been satisfactorily explained. If further treatment i.e., beyond licensure is required, the subject will be referred to the appropriate health care provider.

The following information will be collected during an unscheduled visit.

Unscheduled Visit		
Step	Procedure	Details
U.1	Reason for unscheduled visit	Indicate if the only reason for the visit is that the subject requires additional test articles. If the reason is other than resupply of previously dispensed lenses, specify the reason for the visit.
U.2	Chief Complaints (if applicable)	Record the subject's chief complaints for reasons for the unscheduled visit.
U.3	Adverse Events and Concomitant Medications Review (if applicable)	Review any changes to the subject's medical history or concomitant medications from the previous study visit. Record any changes, and any adverse events.
U.4	Entrance VA (if applicable)	Record the entrance distance visual acuity (OD, OS) to the nearest letter.
U.5	Subjective Sphero-cylindrical Refraction (if applicable)	Perform bare-eye subjective sphero-cylindrical refraction with a phoropter (adopt the maximum plus to maximum visual acuity (MPMVA) approach and use the duo-chrome test for binocular balancing) and record the best corrected distance visual acuity to the nearest letter (OD, OS).
U.6	Slit Lamp Biomicroscopy (if applicable)	FDA Slit Lamp Classification Scale will be used to grade the findings. If the clearance of the fluorescein needs to be expedited, preservative-free rewetting drops may be instilled.  Limbal and Bulbar Conjunctival Hyperemia findings (████████) and Corneal Staining Assessment (████████) will be emphasized using a more detailed scale.  After the slit lamp examination, at the discretion of the Investigator, rinse the subject's eyes thoroughly with rewetting drops or saline.

# Clinical Study Protocol

## Johnson & Johnson Vision Care, Inc.

Unscheduled Visit			
Step	Procedure	Details	
U.7	Dispensing (if applicable)	If the subject requires additional lenses to complete the wear period and is eligible to do so, provide additional lenses per the dispensing instructions given in the detailed study procedures.	
U.8	Exit Visual Acuity (if applicable)	Record the subject's exit distance visual acuity (OD, OS) to the nearest letter.	

**Note:** If the only reason for the unscheduled visit is that the subject requires additional test articles, only the dispensing information needs to be recorded.

